Dose Level	BMS-986156 Part A and Part B	Nivolumab Only Part B
-1	3 mg	240 mg IV Q2W
1	10 mg	240 mg IV Q2W
2	30 mg	240 mg IV Q2W
3	100 mg	240 mg IV Q2W
4	240 mg	240 mg IV Q2W
5	800 mg	240 mg IV Q2W

Abbreviations: IV, intravenous; MAD, maximum administered dose; MTD, maximum tolerated dose; PK, pharmacokinetics; Q2W, every 2 weeks.

¹ Babb 1998; Neuenschwander 2008.

- a Additional subjects may be added for a total of up to 12 subjects per selected dose levels to provide additional safety, tolerability and PK data. This information will be incorporated into final recommendation for MAD/MTD/alternate dose(s) of BMS-986156
- b Dose -1 (3 mg) will be evaluated if 10 mg (dose level 1) exceeds MTD
- c Starting dose for Part B will be one dose level lower than a dose already tested and shown to be tolerated in ongoing monotherapy dose escalation in Part A ([Section 1.1.4](#) for details)

Cohort Expansion (Parts C, D, and E): The purpose of cohort expansion is to gather additional safety, tolerability, preliminary efficacy, PK [REDACTED] information regarding BMS-986156 as monotherapy or in combination with nivolumab.

Continuous evaluation of toxicity events in the cohort expansions will be performed throughout enrollment in the expansion cohorts. If, at any time, the aggregate rate of treatment-related toxicities meeting DLT criteria exceeds 33% across all subjects treated in the Part C cohort expansions, the findings will be discussed and further enrollment may be interrupted. Depending on the nature and grade of the toxicity and after assessing the risk: benefit ratio, a new dose(s) for all cohorts may be initiated at a previously tested lower dose level or at a dose level intermediate to previously tested lower dose levels.

Part C consists of cohort expansions with BMS-986156 monotherapy in 2 disease-restricted populations: (i) NSCLC subjects with progressive or recurrent disease (per RECIST v1.1) during or after anti-PD-1 or anti-PD-L1 therapy following prior platinum doublet-based chemotherapy and (ii) persistent, recurrent or metastatic cervical cancer.

Part D consists of cohort expansion with BMS-986156 administered in combination with nivolumab in disease-restricted populations as follows: (i) NSCLC, (ii) cervical, (iii) bladder cancer, (iv) squamous cell carcinoma head and neck, (v) ovarian cancer, and (vi) hepatocellular carcinoma.

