Dose levels to be considered for the next cohort will be based on evaluating three potential recommendations by BLRM (-Copula): escalate, de-escalate, or stay at same dose level. Final dose selection for next cohort/dose level will be made in conjunction with the data available on all dosed subjects, including clinical and laboratory safety assessments, PK, [REDACTED] data, will not allow escalation by more than one dose level and will be made after discussion and agreement between Investigators and Medical Monitor. Accordingly, intermediate or lower doses, or less frequent dosing of BMS-986156 may be tested if none of the planned doses/schedules is found to be tolerated as monotherapy or in combination with nivolumab. Up to an additional 9 subjects may be enrolled in an already DLT cleared cohort to collect additional PK, [REDACTED] and safety data to better understand any dose response relationship.

Approximately 30 subjects each will be treated in each dose escalation phases in monotherapy (Part A) and combination therapy (Part B).

During dose escalation phase, once a dose level has been decided, a set of approximately 3 subjects will be treated at that specified dose level. Cohort tolerability assessment and subsequent dose recommendation will occur according to BLRM (-Copula) recommendation and after at least 2 subjects complete the 4 week DLT observation period. If the potential DLT occurring in the 3rd evaluable subject regarding the specific dose level does not influence the dose recommendation by BLRM (-Copula), the BLRM (-Copula) recommended next dose level may proceed without waiting for the 3rd subject to complete the corresponding DLT observation period, after discussion and agreement between Sponsor and Investigators.

Subjects must be observed for a total of 28 days following the first therapy dose to be considered evaluable for DLT. Subjects discontinued during DLT observation period due to DLT are also considered as evaluable for DLT. Continuous re-assessment of dose recommendation by BLRM (-Copula) will also be carried out at each dose levels.

The MTD/MAD/alternate dose(s) of BMS-986156 selected for cohort expansion in Parts C and D will be based on evaluating the recommendation from BLRM and a synthesis of all available data, including clinical and laboratory safety assessments, PK, [REDACTED] and efficacy data, from all treated patients at each dose level up to the MTD/MAD.

No intra-subject dose escalation or reduction is allowed.

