3.6.1 Safety observation time for Q4W dosing

Part E will consist of an initial safety lead in period of up to 12 subjects. Six subjects need to complete the 14 day observation period before the full expansion cohorts, of up to 40 subjects, are opened. Patients who discontinue for reasons other than disease progression, death, or treatment-related toxicity may be replaced. An observation period of 14 days has been chosen based on pharmacokinetic (PK) modeling and simulation for BMS-986156, based on PK parameters derived from preclinical studies. [REDACTED]

In part E, BMS-986156 will be evaluated at a dose of 480 mg every 4 weeks (Q4W) with nivolumab 480 mg Q4W. The BMS-986156 480 mg Q4W dose is much lower than the already assessed safe dose of 800 mg Q2W dose (given as monotherapy and combination with nivolumab 240 mg Q2W). Additionally, PK predictions indicate that BMS-986156 concentrations during the first 2 weeks after treatment with 480 mg Q4W will be higher than those achieved by first 240 mg Q2W dose of BMS-986156 Figure 3.6.1-1. However, BMS-986156 levels after first 480 mg dose will be markedly lower than the C_{max} achieved after 1st or 2nd dose of 240 mg BMS-986156 within 7 days, as indicated by the dotted lines below in Figure 3.6.1-1. A similar trend is expected for nivolumab 480 mg Q4W when compared with nivolumab 240 mg Q2W. Although levels of BMS-986156 and nivolumab with 480 mg Q4W dosing regimens are predicted to be lower than the concentrations achieved after 2nd dose with Q2W dosing within 7 days, an additional 7 day safety margin was included to give a 14 day safety observation period was chosen. This measure ensures that nivolumab concentrations will be well below the C_{max} seen with the tested 240 mg nivolumab plus BMS-986156 combination dose evaluated in part D [REDACTED]. A strict safety monitoring in patients will continue throughout the study.

Figure 3.6.1-1: Predicted BMS-986156 concentrations with Q2W and Q4W dosing using a preliminary pharmacokinetic model

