3.7 Stopping Rules During Cohort Expansions

Continuous evaluation of toxicity events in the cohort expansions will be performed throughout enrollment in the expansion cohorts. If at any time, the aggregate rate of treatment-related toxicities meeting DLT criteria exceeds 33% across all subjects treated across all cohorts treated within monotherapy and combination therapy phases at the same dose, the findings will be discussed and further enrollment may be interrupted. If an expansion cohort is discontinued due to toxicity, a new cohort at a previously tested lower dose level, or an alternate treatment regimen (see [Table 3.4.1-1](#)) may be considered based on the aggregate safety experience and in consultation and agreement between Investigators and Sponsor.

All safety signals throughout the conduct of the study will be reviewed by the BMS-986156 Medical Surveillance Team (MST). If unexpected safety findings are identified between scheduled MST meetings, an ad hoc meeting will be convened as appropriate.

Efficacy and safety will be continuously monitored and go/no go decision will be made by discussion with sponsor based on totality of data after assessing benefit/risk ratio in combination with clinical judgement.

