8.1.2 Cohort Expansion

Part C contains 2 cohorts of 25 subjects each in monotherapy cohort expansion,. Each cohort in the combination cohort expansion phase (parts D and E) will contain approximately 40 subjects. Forty subjects in parts D and E are planned with the goal of achieving a width of approximately 20% in the 95% confidence interval for ORR, and to provide additional information on safety. Patients in any cohort who discontinue for reasons other than disease progression, death, or treatment-related toxicity may be replaced.

For initial safety evaluation of 480 mg BMS-986156/480 mg nivolumab Q4W in Part E, 6 subjects will be enrolled and followed for a minimum of 2 weeks (please refer to [Section 3.6](#) for the rationale for 2 week period) prior to opening Part E to full enrollment.

If in a cohort of 40 subjects, 10 or 15 responses are observed, then the lower limit of the one-sided 90% CI for the ORR would be 16%, and 27% respectively. These calculations are made using the Clopper-Pearson method for exact confidence intervals. If the true ORR in a tumor type is 40%, then with 40 subjects there is 93% chance of observing at least 12 responses, and 87% chance of observing at least 13 responses, and there is 7% chance of observing 11 or fewer responses.

Continuous interim evaluations and monitoring of safety and efficacy based on the totality of data will be carried out throughout the expansion phase. Decisions regarding continuing enrollment based on these evaluations will be made through discussion between the Sponsor and investigators based on totality of data and overall clinical activity (such as but not limited to duration of response, quality of response, clinical assessment of response and/or SD and safety). The number of subjects receiving treatment of the planned sample size is approximate and may exceed the specified numbers due to unknown time to response and true recruitment rate (i.e additional participants may be enrolled to compensate the 25%-35% of the screening failure rate in combination with the non response evaluable rate to account for participants who may drop out of the study without being evaluable for response and/or true recruitment rate is much higher than anticipated and thus, Sponsor will examine on the totality of data to determine the benefit/risk ratio as well as overall clinical activity when making the final Go/no Go decision.

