3 DECISION RULE FOR DOSE ESCALATION AND SIMULATION

3.1 Parameters for Dose Recommendation Decision for the Monotherapy and Combination Therapy

In Parts A and B, the BLRM and BLRM-Copula models will be utilized for dose recommendations after DLT information becomes available for each dose cohort and each dose level. Final dose selection for the next dose cohort will be based on BLRM (-Copula) dose recommendations in combination with the totality of data available on all dosed subjects, after discussion and agreement between investigators and the BMS Medical Monitor.

The Bayesian Logistic Regression Method (BLRM) with an overdose control principle (escalation with overdose control [EWOC]) was selected as an appropriate design for the dose escalation parts of this study for the monotherapy setting. For the combination setting, the BLRM-Copula model, which is an extension of the BLRM design, will be utilized. BLRM (-Copula) is similar to the rule-based method (ie, 3 + 3 design) in that the cohort size is approximately 3 subjects for each subject cohort and the toxicity boundaries are set at a minimum 16% (~ 1 in 6) dose-limiting toxicity (DLT) rate and a maximum 33% (~ 1 in 3) DLT rate. These boundaries were chosen in order to target a dose that has meaningful activity but not unacceptably high toxicity. A minimum 16% DLT rate ensures that the model does not guide to use of too low a dose and sacrifice opportunity for benefit without meaningful improvement in safety. The 33% maximum is chosen as this would be the maximum DLT rate where a positive benefit/risk ratio is likely to be demonstrated.

Compared with the rule-based method, when recommending the next dose level, BLRM offers more accuracy and efficiency in determining the true MTD by incorporating historical data and all previous on-study DLT data. The BLRM model also quantifies the benefit and risk during the dose level decision making process. When DLT data are incorporated into the model, the distribution of predicted DLT rates (based on posterior estimation) for a specific dose level will be updated accordingly. The predicted DLT rates will be categorized according to the following 3 categories:

- “under-dosing” defined as a predicted DLT rate between 0% and up to 16%
- “target dosing” defined as a predicted DLT rate between over 16% and up to 33%
- “overdosing” defined as a predicted DLT rate between over 33% and 100%

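### In Part E, newly dosed subjects can temporarily dilute the 33% toxicity trigger when lead-in DLTs first appear after Day 14

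*Combined protocol and SAP*

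**What the plan says.** Section 3.7, with the same words in section 3.5, sets the expansion trigger. It is met if, whenever looked at, the pooled rate of drug-related events that qualify as DLTs "exceeds 33% across all subjects treated across all cohorts treated within monotherapy and combination therapy phases at the same dose". Crossing it leads to discussion and a possible interruption of enrollment. Section 8.2 counts a subject as treated after one dose.

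The synopsis (Cohort Expansion) gives a narrower rule. There the trigger is met if the rate "exceeds 33% across all subjects treated in the Part C cohort expansions, the findings will be discussed and further enrollment may be interrupted". Parts D and E are not named.

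For Part E (480 mg of each drug every 4 weeks), section 3.6.1 says: "Six subjects need to complete the 14 day observation period before the full expansion cohorts, of up to 40 subjects, are opened". The lead-in may hold up to 12 subjects. No limit on lead-in DLTs is stated for opening.

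For dose escalation, section 3.4.1 ties the denominator to follow-up: "Subjects must be observed for a total of 28 days following the first therapy dose to be considered evaluable for DLT". It adds: "Subjects discontinued during DLT observation period due to DLT are also considered as evaluable for DLT". Neither 3.5 nor 3.7 uses that definition.

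Appendix 1, section 3.1 describes the upper toxicity boundary for escalation as "a maximum 33% (~ 1 in 3) DLT rate".

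**The concern.** A DLT enters the numerator when it occurs, but a subject enters the denominator on the day of the first dose. While a cohort is filling, many treated subjects have had little time to show a DLT, so the crude rate understates the rate among subjects with adequate follow-up.

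Part E is the most exposed. Its lead-in is half the 28-day window used in Parts A and B, so Days 15-28 of the lead-in can coincide with open enrollment into two cohorts of about 40. The same-dose condition leaves no mature data in the pool, because no other part uses 480 mg.

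At stake is whether the one numerical prompt for discussion works while pausing enrollment can still spare subjects. If it stays silent, the prompt has to come from review with no stated threshold. Section 7 provides no data monitoring committee.

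**Working it through.** **Inputs.** Limit 33%, all-treated denominator (3.5, 3.7); six lead-in subjects, 14 days (3.6.1, 8.1.2); lead-in of up to 12 (3.6.1); 28-day DLT window (3.4.1 and 3.6, written for Parts A and B). The 33% is a chosen limit, so there is no derived figure to reproduce. Accrual, DLT onset and true DLT rates are not in the documents and are assumed below.

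**1. Dilution.** With k DLTs among six lead-in subjects and m new subjects without a DLT, the rule reads k/(6 + m). For k = 3:

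| m | Rate | Above 0.33? | Above 1/3? |
|---|---|---|---|
| 0 | 3/6 = 50.0% | yes | yes |
| 2 | 3/8 = 37.5% | yes | yes |
| 3 | 3/9 = 33.3% | yes | no |
| 4 | 3/10 = 30.0% | no | no |
| 8 | 3/14 = 21.4% | no | no |

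With 12 in the lead-in, 6/12 = 50% becomes 6/19 = 31.6% after seven new subjects.

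**2. Accrual.** Assume the six are dosed together, enrollment opens on Day 14 and new subjects have no DLT yet. By Day 28, m = 2 × weekly accrual. One per week gives 3/8 (crosses), two give 3/10 (does not), four give 3/14 (does not). At four per week, 4 of 6 (67%) reads 4/14 = 28.6%.

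**3. Timing.** Step 2 is a Day-28 snapshot, but the rule can cross earlier. I simulated onset with half or 75% of DLTs falling by Day 14. Given 3 of 6 lead-in DLTs at two per week, the existing rule has crossed by Day 28 in 42-82% of cases if the limit is 1/3, and in 76-100% if it is a literal 0.33. The second range is higher because 2/6 = 33.3% already exceeds 0.33. Full dilution needs nearly all the DLTs to come late.

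**4. A fixed lead-in check.** Take more than 1/3 of six, that is, at least 3.
- True rate 20%: 1 − (0.8⁶ + 6·0.2·0.8⁵ + 15·0.2²·0.8⁴) = 1 − (0.2621 + 0.3932 + 0.2458) = 9.9%.
- True rate 10%: 1.6%.
- True rate 40%: 45.6%. If all the DLTs were late and four DLT-free subjects had been added, the all-treated rule would need 4 of 6: 15·0.4⁴·0.6² + 6·0.4⁵·0.6 + 0.4⁶ = 17.9%.
- True rate 50%: 65.6% against 34.4% on the same comparison.

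For a lead-in of 12, more than 1/3 means at least 5. At a true rate of 20% this has probability 1 − Σ(j = 0 to 4) C(12, j)·0.2ʲ·0.8¹²⁻ʲ = 1 − 0.9274 = 7.3%.

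**5. Comparison of rules.** Simulation settings: 2,000 trials per setting, 80 subjects, six dosed on Day 0, the rest from Day 14 at 1, 2 or 4 per week, DLTs only within 28 days, limit 1/3, at least six in the denominator. At a true rate of 20%, the chance of at least one crossing is:
- all-treated rule: 8-25%
- all-treated rule plus fixed lead-in check: 13-25%
- DLT-evaluable-only denominator: 36-67%

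At a true rate of 40% with half of DLTs by Day 14, mean subjects treated at first crossing (1/2/4 per week) is 16/22/35 for all-treated and 13/14/16 for evaluable-only. With a literal 0.33 limit, the gap at four per week shrinks to about 26 against 16.

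**The case against.** The strongest reply is that this is a passing feature of a soft trigger. The rule runs continuously, so it may cross before dilution sets in (step 3). New subjects contribute their own DLTs as they are followed. Crossing obliges only discussion. Without a crossing, a subject with a DLT still has drug held (4.3.4) and usually stops permanently (4.3.6), SAEs are reported within 24 hours (6.1.1), and the Medical Surveillance Team reviews all signals and can meet ad hoc (3.7). Prior risk also looks low: section 1.6 reports no DLTs in 34 monotherapy subjects up to 800 mg, and 3.6.1 places 480 mg every 4 weeks well below the 800 mg every-2-weeks dose already assessed.

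All of this stands as a limit on size. It does not repair the denominator, and the earlier combination experience used nivolumab 240 mg, not 480 mg.

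A reader might infer three stronger things that the documents do not support:
- *Late lead-in DLTs would go unreviewed.* The parallel review above says otherwise.
- *The 14-day lead-in is an error.* Section 3.6.1 gives a pharmacokinetic rationale, partly redacted, and the 28-day window is written for Parts A and B.
- *The evaluable-only denominator is the right one.* It counts events at once and makes event-free subjects wait 28 days, so it overstates the rate during accrual. It would cross in 36-67% of trials at a true rate of 20%, which Appendix 1 classes as target dosing.

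**Conclusion.** The point stands in a limited form. The written rule has no follow-up requirement, and nothing elsewhere in the protocol corrects for that. In Part E, 3 late DLTs in six (50%) can read as 30% after four new DLT-free subjects. That requires late onset and, on the assumptions in step 2, accrual of about two per week; at one per week the rule still crosses. The ratios are exact, but how often dilution would occur rests on assumed accrual, onset and true rates. The consequence is a delayed or missed prompt for discussion, not a loss of safety oversight.

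Separately, the synopsis rule, limited to Part C, conflicts with 3.5 and 3.7. That holds whatever view is taken of dilution.

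**What to change.** 1. Keep the all-treated 33% rule in 3.5 and 3.7.
2. Add a Part E check: the proportion of lead-in subjects with a DLT through Day 28, over a fixed denominator (six, or up to 12 if more are enrolled in the lead-in). Discussion follows if more than one in three have a DLT: at least 3 of 6, or at least 5 of 12. Say in advance how a replaced lead-in subject is counted.
3. State the limit as 1/3, so that 2 of 6 does not trigger.
4. Correct the synopsis rule to match 3.5 and 3.7 and to cover Parts C, D and E.

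**Cost.** Wording only: no added subjects, no new data and no delay in opening Part E. The price is a few extra reviews: the lead-in check is met 9.9% of the time with six subjects at a true rate of 20%, and the chance of any crossing goes from 8-25% to 13-25%. Its reach is also limited, since six subjects at a true rate of 40% meet it only 45.6% of the time.

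An evaluable-only rate, a 28-day lead-in or a DLT limit for opening are options for the sponsor to weigh, not corrections.

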3.8 Post Study Access to Therapy

At the end of the study, BMS will not continue to provide BMS-supplied study drug to subjects and investigators unless BMS chooses to extend the study. The investigator should ensure that the subject receives appropriate SOC to treat the condition under study.

3.9 Study Population

For entry into the study, the following criteria MUST be met prior to dosing on Day 1. No exceptions will be granted.

3.9.1 Inclusion Criteria

1) Signed Written Informed Consent

- a) The subject must sign the ICF prior to the performance of any study-related procedures that are not considered part of standard of care.

2) Target Population

- a) Subjects must be at least 18 years old and have histologic or cytologic confirmation of a malignancy that is advanced (metastatic and/or unresectable) with measureable disease per RECIST v1.1 (See [Appendix 3](#)).
- b) **Dose Escalation:** Parts A and B
 - 1) Subjects must have received, and then progressed or been intolerant to, at least one standard treatment regimen in the advanced or metastatic setting, if such a therapy exists. Subjects who refuse or are ineligible for standard therapy will be allowed to enroll provided their refusal/ineligibility is documented in medical records.
 - 2) All solid tumor histologies will be permitted except for subjects with primary central nervous system (CNS) tumors, or with CNS metastases as the only site of active disease.
- c) **Cohort Expansion: Parts C, D and E**
 - 1) Presence of at least one lesion with measurable disease as defined by RECIST v1.1 for solid tumors for response assessment. Subjects with lesions in a previously irradiated field as the sole site of measurable disease will be permitted to enroll provided the lesion(s) have demonstrated clear progression and can be measured accurately.
 - 2) Subjects with prior exposure to therapy with any agent specifically targeting checkpoint pathway inhibition (such as anti-PD-1, anti-PD-L1, anti-PDL-2, anti-LAG-3, anti-CTLA 4 antibody) are permitted after a washout period of any time greater than 4 weeks from the last treatment.

Note:

- (i) *Subjects who experienced prior Grade 1 to 2 checkpoint therapy-related immune-mediated AEs must have confirmed recovery from these events at the*

time of study entry, other than endocrinopathies treated with supplementation, as documented by resolution of all related clinical symptoms, abnormal findings on PE, and/or associated laboratory abnormalities. Where applicable, these subjects must also have completed steroid tapers for treatment of these AEs by a minimum of 14 days prior to commencing treatment with study therapy.

(ii) Eligibility of subjects with prior \geq Grade 3 checkpoint therapy-related immune AEs, will be considered on a case-by-case basis after discussion with the Medical Monitor (eg, asymptomatic isolated grade 3 lipase elevations without clinical or radiological features of pancreatitis will be permitted to enroll).

(iii) In an effort to limit confounding factors, for all cohorts where applicable, no more than 5 subjects previously found to be “rapid progressors” on anti-PD-1 or anti-PD-L1 therapy will be enrolled per cohort.

d) Eastern Cooperative Oncology Group (ECOG) performance status \leq 1

e) Subjects with prior therapy with any agent specifically targeting T-cell co-stimulation pathways except such as anti-GITR antibody, anti- CD137, anti-OX40 antibody, are permitted after a washout period of any time greater than 4 weeks from the last treatment.

f) **Prior palliative radiotherapy must have been completed at least 2 weeks prior to first dose** of study drug. Subjects with symptomatic tumor lesions at baseline that may require palliative radiotherapy within 4 weeks of first dose of study drug are strongly encouraged to receive palliative radiotherapy prior to enrollment.

The following tumor types will be explored:

i. NSCLC Cohort 1 (Part C) and Cohort 3 (Part D): Cohort 10 (Part E)

- 1) Not applicable per Revised Protocol 2
- 2) All subjects with non-squamous histology must have known EGFR and ALK status.
- 3) Subjects with an activating EGFR mutation must have received an EGFR TKI.
- 4) Subjects with an ALK translocation must have received an ALK inhibitor.
- 5) NSCLC subjects with progressive or recurrent disease (per RECIST v1.1) during or after anti-PD-1 or anti-PD-L1 therapy following prior platinum doublet-based chemotherapy

ii. Cervical Cancer Cohort 2 (Part C) ,Cohort 4 (Part D) and Cohort 9 Part E

- 1) Persistent, recurrent or metastatic cervical cancer with documented disease progression
- 2) Squamous, adenosquamous or adenocarcinoma histology - confirmation of the original primary tumor is required
- 3) Must have had at least one prior platinum based regimen
- 4) Confirmation of tumor HPV status: Prior testing results are acceptable if known. If tumor HPV status is unknown, subjects must consent to allow their submitted archived tumor tissue sample in the form of block or unstained slides to be tested for confirmation of tumor HPV status. Both HPV positive and negative subjects are eligible to enroll.

iii. Bladder Cancer - Cohort 5

- 1) Histological or cytological evidence of metastatic or surgically unresectable transitional urothelium involving the bladder, urethra, ureter, or renal pelvis.
- 2) Minor histologic variants (< 50% overall) are acceptable.
- 3) Subjects must have metastatic or surgically unresectable disease.
- 4) Subjects must have progression or recurrence after treatment:
 - With at least 1 platinum-containing chemotherapy regimen for metastatic or surgically-unresectable locally advanced urothelial cancer
 - Within 12 months of peri-operative (neo-adjuvant or adjuvant) treatment with a platinum agent in the setting of cystectomy for localized muscle-invasive urothelial cancer

iv. SCCHN (oral cavity, pharynx, larynx) -Cohort 6

- 1) Documentation of p16-is sufficient to determine human papillomavirus (HPV) status of tumor for SCCHN of the oropharynx. Note: If results are not available, then a sample (tissue on microscopic slides, tissue block or a fresh tissue biopsy in formalin) should be sent to the central laboratory for analysis
- 2) Patients must have had treatment with a platinum containing regimen and evidence of progression or recurrence within six months of last dose of platinum therapy.
- 3) Radiation therapy must have been completed at least 4 weeks prior to study drug administration.
- 4) Histologically confirmed incurable locally advanced, recurrent, or metastatic squamous cell carcinoma head and neck (oral cavity, pharynx, larynx), stage III/IV and not amenable to local therapy with curative intent (surgery or radiation therapy with or without chemotherapy).
- 5) Not applicable in revised protocol 03.

- 6) Prior curative radiation therapy must have been completed at least 4 weeks prior to study drug administration. Prior focal palliative radiotherapy must have been completed at least 2 weeks before study drug administration.
 - 7) Not applicable per Revised Protocol 2
- v. Ovarian Cancer - Cohort 7** (including epithelial OC, primary peritoneal, or fallopian tube carcinoma)
- 1) Histologically- or cytologically-confirmed OC (including epithelial OC, primary peritoneal, or fallopian tube carcinoma) with documented disease progression
 - 2) Documented BRCA mutation status, if known. However, if unknown, subjects must consent to allow their submitted archived tumor tissue sample (block or unstained slides) to be tested. Patients can enroll regardless of BRCA mutation status.
 - 3) Prior therapy requirement: Subjects must have received and then progressed or have been intolerant or refractory to at least 1 standard systemic therapy (eg, platinum-based chemotherapy) for metastatic and/or unresectable disease. Subjects who are sensitive to platinum must have received at least 2 prior platinum-containing lines of treatment.
- vi. Hepatocellular Carcinoma - Cohort 8**
- 1) Subjects must have progressive disease, or been intolerant to, at least one line of therapy or refuse treatment with sorafenib.
 - 2) Child-Pugh score of 6 points or less and must not have encephalopathy and total bilirubin $\leq 1.5 \times$ upper limit of normal (ULN; ie, Child Pugh A)
 - 3) Subjects must have testing for hepatitis B surface antigen (HBsAg), hepatitis B surface antibody, hepatitis B core antibody, hepatitis B DNA polymerase chain reaction (PCR), hepatitis C antibody, or hepatitis C RNA PCR.
 - 4) Subjects with hepatitis B infection must have hepatitis B DNA viral load < 100 IU/mL and must be on anti-viral therapy per institutional guidelines.
 - 5) Subjects with hepatitis B infection must not have co-infection with hepatitis C or hepatitis D (must obtain hepatitis D antibody testing).
 - 6) Subjects must not have clinically significant ascites or clinically significant variceal bleeding.
- vii. Solid tumors types as listed in part D are a part of Cohort 10, Part E**
- 1) Subjects with NSCLC (prior I/O therapy), bladder, SCCHN, ovarian cancer and hepatocellular cancer. Must meet inclusion criteria listed in part D. Must not meet exclusion criteria
 - 2) Must have received, and then progressed or been intolerant to, at least one standard treatment regimen in the advanced or metastatic setting, if such a therapy exists must meet inclusion criteria as stated above. Subjects who refuse or are

ineligible for standard therapy will be allowed to enroll provided their refusal/ineligibility is documented in medical records

h) Conditions for all tumor types

- 
- 2) Not applicable for revised protocol 03
 - 3) Subjects must have ≤ 5 prior treatment regimens. The following are not considered separate lines of treatment: addition of a compound to an on-going regimen, re-starting the same regimen after a drug holiday, or switching from IV to oral therapy.

Parts A-E:

Not applicable as of revised protocol 03.

Adequate organ function for subjects with solid tumor histologies, which is defined as follows:

- 1) White blood cell $\geq 2000/\mu\text{L}$ (stable off any growth factor within 4 weeks of first study drug administration)
- 2) Neutrophils $\geq 1500/\mu\text{L}$ (stable off any growth factor within 4 weeks of first study drug administration)
- 3) Platelets $\geq 100 \times 10^3/\mu\text{L}$ (transfusion to achieve this level is not permitted within 2 weeks of first study drug administration) subjects with hepatocellular cancer $\geq 60 \times 10^3/\mu\text{L}$
- 4) Hemoglobin $\geq 8.5 \text{ g/dL}$ (transfusion to achieve this level is not permitted within 2 weeks of first study drug administration)
- 5) Alanine aminotransferase (ALT) and aspartate aminotransferase (AST) $\leq 3x \text{ ULN}$ subjects with hepatocellular cancer $\leq 5x \text{ ULN}$

- 6) Total bilirubin $\leq 1.5 \times$ ULN (except subjects with Gilbert's Syndrome who must have normal direct bilirubin) subjects with hepatocellular cancer Bilirubin < 3 mg/dL
- 7) Normal thyroid function or stable on hormone supplementation per Investigator assessment
- 8) Serum creatinine $\leq 1.5 \times$ ULN or creatinine clearance (CrCl) ≥ 40 ml/min (measured using the Cockcroft-Gault formula below):
Female CrCl =
$$\frac{(140 - \text{age in years}) \times \text{weight in kg} \times 0.85}{72 \times \text{serum creatinine in mg/dL}}$$

Male CrCl =
$$\frac{(140 - \text{age in years}) \times \text{weight in kg} \times 1.00}{72 \times \text{serum creatinine in mg/dL}}$$
- 9) Albumin > 2.8 mg/dL
- 10) Ability to comply with treatment, PK [REDACTED] sample collection, and required study follow-up.
- 11) Subject Re-enrollment: This study permits the re-enrollment of a subject that has discontinued the study as a pre-treatment failure (e.g., subject has not been treated). If re-enrolled, the subject must be re-consented.

3) Age and Reproductive Status

- a) Men and women, ages ≥ 18 years at the time of informed consent
- b) Women of childbearing potential (WOCBP) must have a negative serum or urine pregnancy test (urine pregnancy test: minimum sensitivity 25 IU/L or equivalent units of human chorionic gonadotropin [hCG]) within 24 hours prior to the start of study drug.
- c) Women must not be breastfeeding.
- d) WOCBP must agree to follow instructions for method(s) of contraception for the duration of treatment with study drug (s) plus 5 half-lives of study drug plus 30 days (duration of ovulatory cycle) for a total of 23 weeks post-treatment completion.
- e) Males who are sexually active with WOCBP must agree to follow instructions for method(s) of contraception for the duration of treatment with study drug (s) plus 5 half-lives of study drug (s) plus 90 days (duration of sperm turnover) for a total of 31 weeks post treatment completion.
- f) Azoospermic males and WOCBP who are continuously not heterosexually active are exempt from contraceptive requirements. However WOCBP must still undergo pregnancy testing as described in this section.

Investigators shall counsel WOCBP and male subjects who are sexually active with WOCBP on the importance of pregnancy prevention and the implications of an unexpected pregnancy. Investigators shall advise WOCBP and male subjects who are sexually active with WOCBP on the use of highly effective methods of contraception. Highly effective methods of contraception have a failure rate of $< 1\%$ when used consistently and correctly.

At a minimum, subjects must agree to the use of two methods of contraception, with one method being highly effective and the other method being either highly effective or less effective as listed below:

HIGHLY EFFECTIVE METHODS OF CONTRACEPTION

Highly effective methods of contraception have a failure rate of $< 1\%$ when used consistently and correctly. WOCBP and female partners of male subjects who are WOCBP are expected to use one of the highly effective methods of contraception (listed below). Local laws and regulations may require use of alternative and/or additional contraception methods. Male subjects must inform their female partners who are WOCBP of the contraceptive requirements of the protocol and are expected to adhere to using contraception with their partner. Male subjects are expected to use a condom, in addition to a highly effective method as noted in the list below

- 1) Progestogen only hormonal contraception associated with inhibition of ovulation
- 2) Hormonal methods of contraception including oral contraceptive pills containing combined estrogen and progesterone, vaginal ring, injectables, implants, and intrauterine devices (IUDs), such as Mirena®
- 4) Nonhormonal IUDs, such as ParaGard®
- 5) Bilateral tubal occlusion
- 6) Vasectomized partner with documented azoospermia 90 days after procedure
 - Vasectomy is a highly effective birth control method provided that the partner is the sole sexual partner of the WOCBP study participant and that the vasectomized partner has received medical assessment of the surgical success.
- 7) Intrauterine hormone-releasing system
- 8) Complete abstinence
 - Complete abstinence is defined as the complete avoidance of heterosexual intercourse (refer to Glossary of Terms, [Section 10](#))
 - Complete abstinence is an acceptable form of contraception for all study drugs and must be used throughout the duration of the study treatment (plus 5 half-lives of the study drug(s) plus 30 days).
 - It is not necessary to use any other method of contraception when complete abstinence is elected.
 - Subjects who choose complete abstinence must continue to have pregnancy tests, as specified in [Section 5.1](#).
 - Acceptable alternate methods of highly effective contraception must be discussed in the event that the subject chooses to forego complete abstinence.
 - The reliability of sexual abstinence needs to be evaluated in relation to the duration of the clinical study and the preferred and usual lifestyle of the subject.
- 9) Use a condom in male subjects with female partners.

UNACCEPTABLE METHODS OF CONTRACEPTION

- 1) Periodic abstinence (calendar, symptothermal, and/or post-ovulation methods)
- 2) Withdrawal (coitus interruptus)

- 3) Spermicide only
- 4) Lactation amenorrhea method
- 5) Diaphragm with spermicide
- 6) Cervical cap with spermicide
- 7) Vaginal sponge with spermicide
- 8) Male or female condom with or without spermicide*
- 9) Progestogen-only oral hormonal contraception, where inhibition of ovulation is not the primary mode of action.

